#### **8.2.2 Recording of Adverse Events**

The Investigator must record all adverse events in the Adverse Event Log provided in each patient's eCRF with information about:

- Adverse event

- Date and time of onset
- Intensity
- Causal relationship to IMP
- Action taken to IMP
- Other action taken
- Date and time of outcome (time can be omitted, if applicable)
- Outcome
- Seriousness
- Relation to prostate cancer progression

Each of the items in the Adverse Event Log is described in detail in the following sections.

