9.3.6 Time from Randomization to Failure in Progression-Free Survival

Progression-free survival (PFS) is a composite endpoint consisting of the following conditions:

- Death
- Radiographic disease progression defined as one or more new metastatic skeletal lesions observed on bone scan; one or more new metastatic extra-skeletal lesions at least 1.5 cm in greatest dimension visible on computed tomography or magnetic resonance imaging scan as confirmed by the Investigator.
- Introduction of additional therapy related to prostate cancer treatment including radiation, anti-androgens and second-line treatment. (ATC and MedDRA codes for disease progression are included in Appendix 3)
- PSA failure defined as the time from randomization to the second occasion (must be at least two weeks apart from the first and correspond to consecutive measurements) in which the PSA value fulfills the following criteria:
 - I. An absolute increase of ≥ 5 ng/ml above nadir and
 - II. An increase of > 50 % of nadir

Time to PFS failure is therefore defined as the time, measured in days, from randomization to the first occurrence of one of the above composite endpoint criteria. Patients discontinuing from treatment/withdrawn from the study will be censored at the time of discontinuation/withdrawal. Time to PFS failure will be analyzed using the Kaplan-Meier estimator of the survival function, the Cox regression model for the hazard rate and the log-rank test of the null hypothesis of equal hazard functions, stratified by age group and region. The p-value of the two-sided stratified log-rank test with significance level of 5% will be presented along with plots of the estimated survival functions for the two treatment groups, stratified by age group and region. The estimated hazard ratio and the associated 95% confidence interval and p-value comparing the treatment with Degarelix to Leuprolide will also be presented.

TLF Table: Secondary Endpoint: Time to PFS Failure - FAS

TLF Figure: Survivor Function for Time to PFS Failure - FAS

Page 30 of 51

9.3.7 Testosterone levels at day 28, 168 and 336 in patients treated with degarelix and leuprolide

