Appendix 3 ATC codes and MedDRA terms for disease progression

A list of ATC codes for antiandrogens and additional therapies classified as disease progression are defined below. Please note that the list may be non-extensive.

Table 6 ATC Codes for Antiandrogens

Level 5 codes
L02BB01 Flutamide
L02BB02Nilutamide
L02BB03Bicalutamide
L02BB04Enzalutamide
G03HA01 Cyproterone

Table 7 ATC codes for Additional Therapy

Level 5 codes
L01DB07Mitoxantrone
L01CD02Docetaxel
L01XX11 Estramustine
L01CD01 Paclitaxel
L02AA01 Diethylstilbestrol
L02AA02 Polyestradiol phosphate
L02AA03 Ethinylestradiol
L02AA04 Fosfestrol
L02AB01 Megestrol
L02BG01 Aminoglutethimide
L02BX03 Abiraterone
G01AF11 Ketoconazole

Investigators recording of disease progression are marked as a tick-box on the Adverse Event form in the eCRF. The MedDRA terms to be used for radiation and second line treatment are defined below.

Page 47 of 51

Table 8 MedDRA Codes (preferred terms) for Radiation

10006089	Brachytherapy to prostate	PT
10014442	Electron radiation therapy to prostate	PT
10017683	Gamma radiation therapy to prostate	PT
10034955	Photon radiation therapy to prostate	PT
10061544	Radiotherapy to prostate	PT
10048205	X-ray therapy to prostate	PT
10014435	Electron radiation therapy to bone	PT
10017675	Gamma radiation therapy to bone	PT
10034947	Photon radiation therapy to bone	PT
10062089	Radiotherapy to bone	PT
10048197	X-ray therapy to bone	PT

 Table 9
 MedDRA Codes (preferred terms) for Second Line Treatment

10061916	Prostatectomy	PT
10050756	Radical prostatectomy	PT
10038961	Retro-pubic prostatectomy	PT
10042594	Supra pubic prostatectomy	PT
10044445	Transurethral prostatectomy	PT

The following terms are also to be classified as investigators recording of disease progression, in case the investigator did not check the tick-box, but only recorded the AE.

Table 10 MedDRA Codes (preferred terms) for additional classification of investigators recording of disease progression

10010264	Condition a ggravated	PT
10061818	Disea se progression	PT
10061819	Disea se recurrence	PT
10048669	Terminal state	PT
10051398	Malignant neoplasm progression	PT
10027452	Meta stases to bone	PT
10027459	Meta stases to lymph nodes	PT
10027457	Meta stases to liver	PT
10027458	Meta stases to lung	PT
10027463	Meta stases to pleura	PT
10062194	Metastasis	PT

Page 48 of 51

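### SAP Appendix 3, Table 10 classes adverse-event terms that name no cancer as disease progression, and the SAP never says whether they count as PFS failures

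*SAP*

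**What the plan says.** **PFS definition.** SAP 9.3.6 lists four conditions: death, radiographic progression, additional prostate cancer therapy, and PSA failure. Failure is the "first occurrence of one of the above composite endpoint criteria". The imaging condition reads "Radiographic disease progression defined as one or more new metastatic skeletal lesions observed on bone scan", or new extra-skeletal lesions of a stated minimum size on CT or MRI, as confirmed by the Investigator. Protocol 9.6.3.7 lists the same four conditions.

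**Pointer to the codes.** Inside the additional-therapy bullet, SAP 9.3.6 adds that "ATC and MedDRA codes for disease progression are included in Appendix 3".

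**Appendix 3.** Tables 6 to 9 code anti-androgens, other therapies, radiation and surgery. The appendix also says that "Investigators recording of disease progression are marked as a tick-box on the Adverse Event form in the eCRF". Table 10 is then introduced by "The following terms are also to be classified as investigators recording of disease progression, in case the investigator did not check the tick-box", for cases where only the adverse event was recorded. It has eleven preferred terms. Seven name a malignancy or metastasis. The other four are *Condition aggravated*, *Disease progression*, *Disease recurrence* and "Terminal state".

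**Adverse Event Log.** Protocol 8.2.2 includes the item "Relation to prostate cancer progression" for each adverse event.

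**The concern.** The four terms say that something got worse, came back or became terminal, but not what. Inclusion criterion 8 requires documented cardiovascular disease in every patient, so the condition in question may be cardiac. Table 10 asks for no attribution to prostate cancer, no case review and no exclusion of cardiovascular events. It acts exactly where the investigator left the progression box empty.

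If these records enter PFS, the endpoint gains a fifth component that neither document lists. It would bypass the imaging criterion and could count non-cancer worsening as cancer failure. If they do not enter PFS, Table 10 is an instruction without a stated purpose, and the programmer has to guess. The Clinical Events Classification committee adjudicates cardiovascular events. No blinded review of PFS events is described, and treatment is open-label at the sites, so nothing later in the process would catch a false progression.

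**Working it through.** No document figure can be reproduced: the SAP and protocol give neither a PFS event rate nor a frequency for the Table 10 terms. The check is of the text, followed by an illustration under stated assumptions.

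**1. What the rule overrides.** Appendix 3 describes a progression tick-box on the Adverse Event form. Protocol 8.2.2 describes a log item on relation to prostate cancer progression. The two appear to be the same field, although neither document says so. On that reading, a vague term overrides an unticked cancer-specific box.

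**2. Does Table 10 feed PFS?**

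| Evidence | Points to |
|---|---|
| SAP 9.3.6 and protocol 9.6.3.7 list four criteria; none is an adverse-event term or the tick-box | No |
| The pointer to Appendix 3 sits in the additional-therapy bullet, which Tables 6 to 9 already serve | No |
| The pointer speaks of codes for disease progression, the title of the whole appendix | Yes |
| No other section of the SAP text cites Appendix 3 | Yes |

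The link is suggested but not stated.

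**3. Is it declared?** SAP Section 12 names the revised key secondary endpoints, the change of testing procedure and the reduction after early termination, and refers to the change log. The log entries for versions 5 to 7 do not mention an adverse-event route to progression.

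**4. Illustration of size.** Let *f* be the share of the control-arm PFS hazard that is really non-cancer worsening, HR_p the hazard ratio for true PFS failure, and HR_c the hazard ratio for the contaminating events. With constant hazards,

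HR_obs = (1 − f) × HR_p + f × HR_c.

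All inputs are assumptions. The value 0.49 is borrowed from the design hypothesis for MACE (SAP 3.2); 2.04 is its reciprocal, 1/0.49.

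| HR_p | HR_c | f = 2% | f = 5% | f = 10% |
|---|---|---|---|---|
| 1.0 | 0.49 | 0.990 | 0.975 | 0.949 |
| 1.0 | 2.04 | 1.021 | 1.052 | 1.104 |
| 0.70 | 1.0 | 0.706 | 0.715 | 0.730 |

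Example: 0.95 × 1.0 + 0.05 × 0.49 = 0.975. The shift is small when *f* is small, and its sign depends wholly on HR_c, which the documents do not give for such events.

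**The case against.** The strongest reply is that SAP 9.3.6 already limits failure to four criteria, so a Table 10 term cannot be a PFS event as the SAP stands. That is a fair reading of the list, and it is why the point is conditional. It leaves Table 10 without a use, however, and the only citation of its appendix is in that same section.

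Several features also make the cardiovascular route uncommon:

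- Protocol 8.2.2 asks for adverse events to be recorded as diagnoses. This stands, but only where a diagnosis is available.
- Protocol 8.2.3 captures worsening cardiovascular status separately, and 8.3.2.2 gives myocardial infarction, stroke and unstable angina their own eCRF modules. This lowers the risk. But 8.2.2 still requires all adverse events in the log, and nothing removes cardiovascular events from Table 10's reach.
- Death is already a PFS event, so *Terminal state* would mostly move a failure date earlier. The exception is a patient who would otherwise be censored at discontinuation or withdrawal under SAP 9.3.6. For that patient an earlier record could turn a censored time into a failure.

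A reader might go further and infer that PFS is biased towards degarelix, because false progressions would fall mainly on leuprolide. The documents do not support this. Taking 1–2% of the 545 randomized patients would give 5–11 such events, but nothing anchors that rate; SAP Section 3 reports only 14 patients with positively adjudicated events. Splitting them by 1/(1 + 0.49) = 67% on leuprolide treats the design hypothesis for all-cause death, myocardial infarction or stroke as if it applied to unspecified aggravated conditions.

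**Conclusion.** The point holds as a conditional one. Table 10 classes four terms that name no cancer as investigator-recorded progression when the box is unticked. If it is applied as the pointer in SAP 9.3.6 suggests, it adds an undeclared PFS component that conflicts with the definition in both documents. If it is not, its purpose is undefined. That these terms are in fact counted as PFS failures is an inference and is not stated anywhere.

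The size is unknown and probably small, and the direction cannot be established. PFS is an other secondary endpoint outside the fixed testing sequence (SAP 9.3), and the primary MACE analysis does not use Appendix 3. This is a cheap improvement, with no bearing on the trial's main conclusion.

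**What to change.** 1. In SAP 9.3.6, state that an adverse-event term alone is not a PFS failure unless the death, imaging, therapy or PSA criterion is met. This settles both readings, for the tick-box as well as for Table 10.
2. In Table 10, remove *Condition aggravated*, *Terminal state*, *Disease progression* and *Disease recurrence*, or count them only when the Adverse Event Log item on relation to prostate cancer progression is positive. Removing only the first two would leave two equally unspecific terms. If the log item and the tick-box are the same field, the conditional option makes these rows redundant and removal is simpler.
3. If the sponsor does intend Table 10 to count, list it in 9.3.6 as a PFS component, declare it in Section 12 as a departure from protocol 9.6.3.7, and also report PFS without those events.

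The cost is one sentence and four table rows, or under the third option a few lines and one additional PFS analysis. The downside of the first two steps is that a rare true progression recorded only under a vague term would be missed.

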Appendix 4 ATC codes and MedDRA terms for Prohibited Therapy

A list of ATC codes for prohibited concomitant medication are defined below. Please note that the list may be non-extensive.

Table 11 ATC codes for prohibited concomitant medication

Level 5 codes
L02AB01 Megestrol a cetate
G01AF11 Ketoconazole
L02BX03 Abiraterone
L02BB04Enzalutamide
L02BB01Flutamide
L02BB02Nilutamide
L02BB03Bicalutamide
G03HA01 Cyproterone
L02AA01 Diethylstilbestrol
L02AA02 Polyestradiol phosphate
L02AA03 Ethinylestradiol
L02AA04 Fosfestrol

Additionally all substances in the ATC G03 therapeutic subgroup are considered as prohibited concomitant medications.

Table 12 MedDRA code (preffered term) for prohibited therapy

10049628 Bilateral orchidectomy	PT
---------------------------------	----

Page 49 of 51

Appendix 5 Cardiovascular Endpoint Definitions

Endpoints / Event definitions

The cardiovascular endpoint definitions given below are based on the 2014 Definitions for Cardiovascular Endpoint Events in Clinical Trials¹.

1.1 Death

All deaths will be categorized as Cardiovascular, non-Cardiovascular or Undetermined.

Cardiovascular Death: Cardiovascular Death is defined as death resulting from an acute myocardial infarction, sudden cardiac death, death due to heart failure, death due to stroke, death due to cardiovascular procedures, death due to cardiovascular hemorrhage, and death due to other cardiovascular causes.

Non-cardiovascular Death: Non-cardiovascular death is defined as any death that is not thought to be due to a cardiovascular cause (e.g. cancer related death). Non-cardiovascular deaths will also be sub-classified as related to prostate cancer progression or to other causes.

Undetermined Cause of Death: Undetermined cause of death refers to a death not attributable to one of the above categories of cardiovascular death or to a non-cardiovascular cause, due to absence of any information (e.g., the only available information is "patient died"). Undetermined death will be presumed and analyzed as non-cardiovascular deaths on the secondary analysis.

1.2 Myocardial Infarction

The adjudication of myocardial infarction as a clinical endpoint will consider the occurrence relative to a percutaneous coronary intervention (PCI) or coronary artery by-pass grafting (CABG). (It will also be consistent with the revised American College of Cardiology (ACC) / European Society of Cardiology (ESC) myocardial infarction definition document.)

In the absence of a PCI or CABG, a spontaneous myocardial infarction is defined as:

For patients having a PCI, a myocardial infarction will be defined as:

CK-MB (or troponin I/T or CK in the absence of CK-MB) >3 x ULN for samples obtained within 24 hours of the procedure if the baseline values were normal or at least a 50% increase

over elevated baseline values that were stable or decreasing or development of new pathological Q waves (>0.04 seconds) in at least 2 contiguous leads in the absence of LBBB on the ECG. Symptoms of cardiac ischemia are not required.

After CABG surgery, a myocardial infarction is defined as either:

CK-MB (or CK in the absence of CK-MB) >5 x ULN for samples obtained within 24 hours of the procedure with development of new pathological Q waves in at least 2 contiguous leads in the absence of LBBB on the ECG.

CK-MB (or CK in the absence of CK-MB) > 10 x ULN for samples obtained within 24 hours of the procedure with or without development of new pathological Q waves in at least 2 contiguous leads in the absence of LBBB on the ECG.

Note: For institutions that report an 'intermediate' or 'equivocal' range for biomarker elevation that is not definitively associated with myocardial necrosis or infarction then the ULN should be the lower value for the necrosis or infarct range, not the 'equivocal' or 'intermediate' range lower value.

1.3 Unstable Angina Requiring Hospitalization

1.4 Cerebrovascular Accident (Stroke)

Stroke is defined as an acute focal neurological deficit of sudden onset that is not due to an identifiable non-vascular cause (i.e. brain tumor, trauma, brain procedures, metabolic condition)

Degarelix, FE 200486 Trial Code: 000108 Statistical Analysis Plan Date: 24 Feb 2021 E-Statistical Analysis Plan-19595; Ver.7.0 Supersedes: 6.0

Page 51 of 51

a) that is not reversible within 24 hours or results in death (in <24 hours)

or

b) that resolves in <24 hours and is accompanied by clear evidence of a new stroke on cerebral brain imaging studies (brain Computed tomography [CT] or Magnetic Resonance Imaging [MRI] scans)

Classification:

Ischemic Stroke: is defined as an acute episode of focal cerebral, spinal, or retinal dysfunction caused by central nervous system (CNS) infarction.

Note: Hemorrhage may be a consequence of ischemic stroke. In this situation, the stroke is an ischemic stroke with hemorrhagic transformation and not a hemorrhagic stroke.

Hemorrhagic Stroke: is defined as an acute episode of focal or global cerebral or spinal dysfunction caused by intraparenchymal, intraventricular, or subarachnoid hemorrhage.

Note: Subdural hematomas without new neurologic symptoms are intracranial hemorrhagic events and not strokes.

Undetermined Etiology: is defined as an acute episode of focal or global neurological dysfunction caused by presumed brain, spinal cord, or retinal vascular injury as a result of hemorrhage or infarction but with insufficient information to allow categorization as either ischemic or hemorrhagic.

